## **Objectives**

1. To evaluate the effectiveness of a collaborative stepped care and peer support programme in engaging older people at-risk of or with depression.
2. To evaluate the efficacy of the programme in reducing symptoms/risks and promoting wellbeing in older people at-risk of or with depression.
3. To investigate the impact of the programme on care resources utilization in these older adults.

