## **Methods**

### Design

This study adopts quasi-experimental design and compares older adults at-risk of or with depression receiving the stepped collaborative care (intervention group) versus those receiving standard care (control group).

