### Participants

1. Intervention Group: older people at-risk of having depression (n=1,600) and those with clinically significant depressive symptoms (n=400) recruited from NGOs providing the intervention in four pilot districts in Hong Kong
2. Control Group: older people at-risk of having depression (n=400) and those with clinically significant depressive symptoms (n=100) referred by different NGOs in Hong Kong and recruited through open recruitment

The inclusion criteria are:

- age 60 years or above; and
- residing in Kwun Tong, Kwai Chung, Tseung Kwan O, or Sham Shui Po; and
- have one or more known risk factor(s) for developing depression; and/or
- have depressive symptoms of mild level or above; and
- able to give informed consent to participate

The exclusion criteria are:

- known history of autism, intellectual disability, schizophrenia-spectrum disorder,
- bipolar disorder, Parkinson's disease, or dementia
- (temporary exclusion criteria) imminent suicidal risk;
- and difficulty in communication

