#### Assessment Procedures

After basic screening, assessments will be conducted by trained social services staff and peer supporters employed by NGOs for the intervention group, and by trained research assistants employed by the University of Hong Kong for the control group.

For the intervention group, assessments will be conducted at baseline (T0/Intake), completion of intervention (4 weeks to 6 months, depending on individual condition) or drop-out (T1/Exit), and follow-up at 12 months (T2/FU). For control group, assessment would be conducted at T0 and T2.

Assessment for those with clinically significant depressive symptoms will last for about 90 minutes, and assessment for those at-risk of depression will last for around 60 minutes.

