### Data Analysis

We will generate descriptive statistics of the demographic and clinical variables at the baseline (T0/Intake) assessment. The independent sample t-test will be used to compare the means of continuous variables in the intervention and control groups; the chi-square test will be used to compare categorical variables; and Fisher exact test will be used for variables with low cell counts ( $n < 5$ ). For the majority of clinical scales that are ordinal in nature, the independent samples Mann-Whitney U-test will be used to examine whether the same distributions could

be assumed across groups. As observations at two /three time points are nested within individuals and individuals are nested within clusters (centers), changes in outcome measures, including PHQ-9 and GAD-7 scores, will be assessed by a three-level linear mixed model. Because the number of clusters is small, degree-of-freedom correction using the Satterthwaite method will be applied to the mixed models to maintain the desired type I error rate (Leyrat, Morgan, Leurent, & Kahan, 2017). We will use STATA 14.1 (StataCorp, 2015) for data analysis. For all the tests, the statistical significance level was set at .05.

To investigate engagement in the intervention versus control group, the following analyses will be conducted: (1) Cox proportional hazard regression analysis of the time to the primary endpoint of voluntary withdrawal from service; (2) Chi-square test of initial refusal of service by eligible participants after screening.

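### The non-randomised efficacy comparison is planned with no adjustment for measured differences between the arms

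*Combined protocol and SAP*

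**What the plan says.** The Design section states: "This study adopts quasi-experimental design". Randomisation is not described anywhere. Under Participants, the intervention arm (1,600 at-risk plus 400 symptomatic) is "recruited from NGOs providing the intervention in four pilot districts in Hong Kong". The control arm (400 plus 100) is "referred by different NGOs in Hong Kong and recruited through open recruitment". The Interventions section adds outreach by peer supporters to find hidden cases, for the intervention group only. The same eligibility criteria apply to both arms, including "residing in Kwun Tong, Kwai Chung, Tseung Kwan O, or Sham Shui Po".

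Under Assessment Procedures, the intervention arm is assessed at T0, T1 and T2 (12 months), but "For control group, assessment would be conducted at T0 and T2". NGO staff and peer supporters assess the intervention arm. Controls are assessed "by trained research assistants employed by the University of Hong Kong for the control group".

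The Data Analysis section first compares the arms at baseline with t, chi-square, Fisher and Mann-Whitney tests. For efficacy, "changes in outcome measures, including PHQ-9 and GAD-7 scores, will be assessed by a three-level linear mixed model", with time within person within centre and Satterthwaite degrees of freedom. It lists no fixed effects, covariates, propensity score, weights or matching, and it does not say what follows if the baseline tests show a difference.

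**The concern.** The second objective is causal: "To evaluate the efficacy of the programme in reducing symptoms/risks and promoting wellbeing in older people at-risk of or with depression". Without randomisation, a difference in 12-month change between the arms can come from the programme or from who was recruited. People found by outreach through the delivering NGOs may differ from people who answer an open call or are referred by other organisations. The Measurements section itself lists risk factors for late-life depression, such as bereavement, living alone and disability. Any of these could differ between the arms and also affect natural course.

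If one does, the group-by-time estimate mixes the programme effect with the recruitment difference, in either direction. The plan contains no analysis that would separate the two, and the error does not shrink as the sample grows. Choosing covariates after the results are seen would forfeit the protection of prespecification.

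**Working it through.** **What the plan's own safeguards do**

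- *Modelling change* removes stable differences in level. It leaves differences in course.
- *The centre random effect* does not adjust for person-level characteristics. If each centre contributes to one arm only, as the recruitment text suggests, it cannot separate arm from recruitment source.
- *The Satterthwaite correction* deals with few clusters, not with confounding.
- *The common criteria and the same 80:20 mix* (1,600/2,000 and 400/500) balance broad strata only.
- *The baseline tests* detect imbalance, but nothing follows from them.

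**Size, as an illustration**

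The plan gives no standard deviation, correlation, intraclass correlation or effect size, so there is no figure of its own to reproduce.

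Inputs from the documents: 2,000 versus 500 overall, 400 versus 100 in the symptomatic group, and significance level 0.05 (taken as two-sided).

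Assumed inputs: equal SD at T0 and T2, correlation r = 0.6, complete data, and the prevalences, extra change and design effects (DE) below.

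Both arms share only T0 and T2, so the contrast is the difference in T0-T2 change:

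- SE in SD units = √[2(1 − r)(1/n₁ + 1/n₀) × DE].
- 2,000 v 500, DE 1: √[0.8 × 0.0025] = 0.0447. At DE 2 and 4: 0.0632 and 0.0894.
- 400 v 100, DE 1: √[0.8 × 0.0125] = 0.100.
- Bias = prevalence difference × extra change in carriers. For 30% v 20% and 0.5 SD: 0.10 × 0.5 = 0.05 SD.
- False-positive rate = Φ(−1.96 + bias/SE) + Φ(−1.96 − bias/SE). At DE 1, bias/SE = 0.05/0.0447 = 1.118, which gives 0.201.

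False-positive rates with normal critical values; in brackets, noncentral t with 4 degrees of freedom:

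| Comparison | Bias (SD) | DE 1 | DE 2 | DE 4 |
|---|---|---|---|---|
| 2,000 v 500 | 0.0125 | 5.9% | 5.4% | 5.2% |
| 2,000 v 500 | 0.025 (5 points × 0.5 SD) | 8.6% | 6.8% (6.1%) | 5.9% (5.6%) |
| 2,000 v 500 | 0.05 (10 points × 0.5 SD) | 20.1% | 12.4% (9.5%) | 8.6% (7.2%) |
| 2,000 v 500 | 0.10 (20 points × 0.5 SD) | 60.9% | 35.3% (23.1%) | 20.1% (14.1%) |
| 400 v 100 | 0.05 | 7.9% | 6.4% (5.9%) | 5.7% (5.4%) |

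At bias 0.05 SD and 2,000 v 500, r = 0.4 gives 15.0%, 9.9% and 7.4% at DE 1, 2 and 4; r = 0.8 gives 35.3%, 20.1% and 12.4%.

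**Would the imbalance be seen?** Without clustering, the planned chi-square test would flag 30% v 20% with probability 99.7% at 2,000 v 500 and 51% at 400 v 100.

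**Would adjustment work?** Simulation with no programme effect and no clustering, 2,000 v 500, 20,000 runs:

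- Unadjusted: mean estimate 0.050 SD, SE 0.046, rejection 19%.
- With the covariate-by-time term: mean 0.000, SE 0.045, rejection 5%.

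The term must be an interaction with time. In a random-intercept model with complete T0 and T2 data, adding only the covariate's main effect changed the group-by-time estimate by less than 10⁻¹³.

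**The case against.** The strongest reply is that the section is silent rather than wrong. It does not even list group and time as fixed effects, and nothing in it forbids covariates. The harm is also conditional: a characteristic must both differ between the arms and predict change, and the documents show neither. Milder assumptions give little inflation. A 10-point difference with 0.2 SD extra change gives 0.02 SD of bias and false-positive rates of 5.6-7.3% (DE 4 to 1). Allowing 25% loss in both arms lowers the 20% figure to about 16%. The simulation adjusts for exactly the confounder that it generated, so it confirms the algebra and does not predict performance in this study. Weighting or a baseline-conditioned model would also be a legitimate choice.

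All of this limits the size, and it rules out claiming a known bias. It does not remove the omission. Followed as written, the plan yields an unadjusted non-randomised estimate, and silence leaves the choice of covariates until after the data are seen. Greater clustering or attrition lowers the false-positive rate by widening the interval; neither takes the bias out of the estimate. Unmeasured selection and different assessors by arm would survive adjustment, but that is no reason to leave measured differences uncorrected.

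**Conclusion.** The concern holds. The efficacy comparison is non-randomised, the recruitment routes differ, and no adjustment is prespecified, so any measured difference between the arms that predicts 12-month change would stay in the estimate. Confidence is high for this omission only. The actual bias cannot be calculated from the documents. Across assumed imbalances of 5 to 20 points with 0.5 SD extra change in carriers, the bias is 0.025 to 0.10 SD and the false-positive rate at 2,000 v 500 runs from about 6% to 61%, depending on clustering. It is zero bias and 5% if there is no imbalance. Because the study's efficacy objective depends on this model, the point should be settled before the analysis.

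**What to change.** In the Data Analysis section:

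1. State group, time and group-by-time as fixed effects, with T2 versus T0 as the between-arm contrast.
2. Name as primary the model that adds a short prespecified set of T0 covariates and their interactions with time: age, gender, marital status, education, risk-flowchart items, district and risk group. Code widowhood once, since it appears under both marital status and the flowchart.
3. Add the HK-MoCA 5-Min, UCLA-3 and CSRI service use only if they are collected in both arms and in both the 60- and 90-minute assessments.
4. Keep the Satterthwaite correction, state the number of centres, and keep the district terms only if that number leaves enough degrees of freedom.
5. As sensitivity analyses, report the unadjusted model and a T2 model that also conditions on the T0 outcome score. The second addresses baseline severity and regression to the mean.
6. Report standardised mean differences at baseline. If recruitment source is recorded, repeat the analysis with NGO-referred controls only.
7. State that unmeasured selection and arm-specific assessors still limit the causal conclusion.

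The cost is plan wording and modest analysis work. No new data are needed if the listed variables are recorded at T0 in both arms. Item 6 also needs recruitment source, which the documents do not say is recorded. The downsides are possibly somewhat wider intervals with many covariates or few centres, and sensitivity results that may disagree with the primary one.

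### The plan allows for few centres in its mixed models but states no allowance for centre in the two engagement analyses that carry Objective 1

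*Combined protocol and SAP*

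**What the plan says.** All of the following is in the combined protocol and SAP.

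- **Clustering.** Data Analysis describes repeated observations within individuals, and individuals within centres. It assigns a three-level linear mixed model to changes in outcome measures, including PHQ-9 and GAD-7. It then says: "Because the number of clusters is small, degree-of-freedom correction using the Satterthwaite method will be applied to the mixed models". The reason given is control of the type I error rate.
- **Engagement.** The next paragraph of Data Analysis gives two analyses: "Cox proportional hazard regression analysis of the time to the primary endpoint of voluntary withdrawal from service" and "Chi-square test of initial refusal of service by eligible participants after screening". No frailty, centre stratification, robust variance or small-cluster correction is stated for either, and no other section adds one.
- **Level.** "For all the tests, the statistical significance level was set at .05". This sets the threshold only.
- **Objective served.** Objective 1 is "To evaluate the effectiveness of a collaborative stepped care and peer support programme in engaging older people at-risk of or with depression".
- **Source of participants.** Under Participants, the intervention group (1,600 + 400) is "recruited from NGOs providing the intervention in four pilot districts in Hong Kong". The control group (400 + 100) is "referred by different NGOs in Hong Kong and recruited through open recruitment". Both must live in the same four districts.

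**The concern.** The plan accepts that its centres are few and that ignoring this would disturb the error rate, and it acts on that for the symptom scales only. Engagement is at least as likely to vary by centre. Under Interventions, each NGO's own peer supporters find and engage people, and usual care is decided by the worker in the NGO unit.

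If each centre contributes mainly to one group, a difference between centres in refusal or withdrawal becomes part of the difference between groups. A plain Cox model or chi-square test treats all participants as independent, so its standard error leaves that part out. An ordinary difference between centres could then be declared a programme effect more often than the stated 5%, on the only two analyses that the plan gives for Objective 1.

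**Working it through.** **What can be reproduced.** The documents give no sample-size calculation, number of centres, ICC or event rate, so there is no figure of the plan's own to reproduce. What follows is illustration.

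**Inputs from the documents.** Intervention 1,600 + 400 = 2,000; control 400 + 100 = 500; level .05 (two-sided assumed).

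**Assumed inputs.** Number of centres, ICC, equal-sized centres nested within group, and 2,000 and 500 as the refusal denominators. The simulations also assume a 20% risk of refusal or of withdrawal by 12 months.

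**Formulas.**
- Design effect per group: DE = 1 + (m − 1) × ICC, with m the number of people per centre.
- Variance ratio: r = (DE_I/2000 + DE_C/500) / (1/2000 + 1/500); the denominator is 0.0025.
- Actual type I error: 2 × [1 − Φ(1.96/√r)].

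**Adverse layout, 8 + 4 centres, ICC 0.01.**
- m = 250 and 125; DE_I = 1 + 249 × 0.01 = 3.49; DE_C = 1 + 124 × 0.01 = 2.24.
- r = (0.001745 + 0.00448)/0.0025 = 2.490.
- Type I error = 2 × [1 − Φ(1.242)] = 21.4%.

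**Mild layout, 40 intervention centres, unclustered controls, ICC 0.01.**
- m = 50; DE_I = 1 + 49 × 0.01 = 1.49; DE_C = 1.
- r = (0.000745 + 0.002)/0.0025 = 1.098.
- Type I error = 2 × [1 − Φ(1.870)] = 6.1%.

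**Range of the plain test at nominal 5%.**

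| Layout (intervention + control centres) | ICC 0.001 | ICC 0.01 | ICC 0.05 |
|---|---|---|---|
| 40 + unclustered | 5.1% | 6.1% | 10.8% |
| 8 + 4 | 6.7% | 21.4% | 50.0% |

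At ICC 0 every layout gives 5%. At ICC 0.01 the intermediate layouts give 7.3% (20 + unclustered) and 12.0% (20 + 10). In the symptomatic stratum alone (400 vs 100), ICC 0.01 gives 5.2% to 8.4%. For scale, with a mean refusal of 20%, ICC 0.01 puts the 10th and 90th percentile centres at about 15% and 25%.

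**Simulation check, ICC 0.01, no effect.** With 8 + 4 centres the chi-square test rejects in 21.7% of runs and Cox (score form) in 21.0%. With 40 centres and unclustered controls the figures are 6.5% and 6.2%.

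**If centre and group are not tied.** With the same 8 centres supplying both groups at ICC 0.01, the chi-square test rejects in 5.1% of runs when supply is balanced and 12.5% in one uneven pattern.

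**Unequal time at risk.** Under Assessment Procedures, the intervention ends between 4 weeks and 6 months, while controls are assessed only at baseline and 12 months. If intervention time at risk ended at 1 to 6 months and control time at 12, plain Cox at ICC 0.01 would reject in about 12% of runs (8 + 4) or 7% (8 + unclustered controls).

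**Candidate replacements.**
- Welch t-test on centre refusal proportions: type I error 4.2% to 5.7% across the layouts tried, ICC 0 to 0.05.
- Cluster-robust score test without a few-cluster correction: 5.1% to 18.4%, so not sufficient.
- Welch t-test on centre means of observed-minus-expected withdrawals: 4.6% to 6.4% over a common 12-month window. Over the unequal windows above, its power at hazard ratio 0.7 is only about 5% to 13%, against about 50% for plain Cox.

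**The case against.** The strongest objection is that the size is not anchored in the documents. Centre counts, ICCs, event rates and the true refusal denominator (eligible people after screening, not the enrolment targets) are all assumed. With many centres and unclustered controls, or balanced shared centres, the plain tests are close to nominal. This stands, and it limits what can be said about size. It does not remove the omission, because the plan's own premise is that centres are few.

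A second objection is that adjustment costs power, and that a purely centre-level test gives up participant covariates, which matter in a quasi-experimental study. This also stands, and it bears on the choice of method. For withdrawal it favours keeping a Cox regression over a centre-level test. The figure of about 50% for plain Cox is itself partly inflated in the clustered layouts, but it is also about 50% with 40 centres and unclustered controls, where plain Cox is near nominal.

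A reader might also infer more than the text supports:

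- *That centres are certainly nested within group.* In the control description, *different* may mean *various*, and both groups come from the same districts.
- *That the error rate is 21% or 50%.* Those figures belong to assumed layouts.
- *That withdrawal is the trial's one primary outcome.* The phrase sits inside the Cox sentence and may only name the event being timed. The Objectives designate no primary outcome.
- *That the plan rules out adjustment.* It only fails to state one.

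**Conclusion.** The omission is real. The plan prespecifies an allowance for few centres in its linear mixed models and none for the Cox and chi-square analyses behind Objective 1. If centres differ in engagement and are nested within group, or supply the groups unevenly, the stated standard errors are too small and the tests exceed 5%.

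How far they exceed it cannot be derived from the documents. An illustrative range at ICC 0.01 is about 6% to 21%, falling to 5% to 7% at ICC 0.001 and to about 5% with balanced shared centres. The documents make the link between centre and group probable but do not state it. The point should be acted on, with medium confidence; it does not show that an engagement result would be wrong.

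**What to change.** In Data Analysis, replace the two plain tests with cluster-adjusted analyses that carry a small-cluster correction.

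- **Refusal.** Compare centre-level proportions by a Welch t-test, or use a mixed-effects logistic model with a small-sample correction.
- **Withdrawal.** Keep the Cox regression and its hazard ratio. Add centre as a shared frailty, or use a cluster-robust variance with a few-cluster correction; an uncorrected robust variance is not enough. Either form also admits participant covariates. Do not make the Welch test on observed-minus-expected withdrawals the lead test, because of its power over unequal windows.
- **Definition of centre.** State what the centre is for openly recruited controls (for example, singletons or recruitment route). Record a centre or route code for participants and refusers, and report centres per group and ICCs.
- **Shared NGOs.** If the same NGOs supply both groups, stratification by centre is an option. Openly recruited controls would then contribute nothing to the comparison, and the plan must say so.

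**Cost.** The change needs new wording and one code, with no new outcome data. Intervals widen and power falls when centres are few. For refusal of 20% vs 14.5% with 8 + 4 centres and ICC 0, power falls from about 85% (chi-square) to 59% (Welch). With 40 centres and unclustered controls at ICC 0.01 it falls only from 83% to 78%. For withdrawal at hazard ratio 0.7 over a common window (8 + 4 centres, ICC 0), a centre-level test takes power from about 82% to 56%. No power figure was worked out for the frailty or corrected robust Cox model, so the sponsor should simulate the chosen model at the actual number of centres. Confounding from the non-randomised design remains.

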### Measurements

1. Basic demographics: age, gender, marital status, education (years and highest attainment), and work experience.
2. Risk flowchart: a customized questionnaire for quick screening of the following known risk factors for late-life depression: recent spousal death; widowed; disability; living alone; pain & sleep complaints.
3. The Patient Health Questionnaire (PHQ-9) (Kroenke, Spitzer, & Williams, 2001): a 9-item instrument that incorporates depression diagnostic criteria with other leading major depressive symptoms, and rates the frequency of the symptoms which factors into the scoring severity index. PHQ-9 scores of 5-9, 10-14, 15-19, 20 and above represent mild, moderate, moderately severe, and severe depression.
4. Self-harm risk assessment: assessment by social service staff on participant’s risk of self-harm (yes or no answers to 10 items) and harm to others (yes or no answers to 4 items), and in the end social service staff will give an overall evaluation of suicidal risk score ranging from 0-No to 3-High.

5. Generalized Anxiety Disorder scale (GAD-7; Spitzer, Kroenke, Williams, & Lowe, 2006): a 7-item scale, responses to each item are rated on a 4-point Likert scale and range from 0 to 3. The following guidelines are recommended for the interpretation: 5-9 for mild anxiety, 10-14 for moderate anxiety, and 15-21 for severe anxiety.
6. Hong Kong Montreal Cognitive Assessment 5-Minute Protocol (HK-MoCA 5-Min) (Wong et al., 2015): a validated and reliable cognitive screen for stroke and transient ischemic attack, brief and highly feasible for telephone administration. It includes four items examining attention, verbal learning and memory, executive functions/language, and orientation extracted from the MoCA.
7. Name generator: asking participants to list out names of people who they would turn to when they feel down, and when they need help for trivial things.
8. UCLA loneliness scale (UCLA-3) (Hughes, Waite, Hawkley, & Cacioppo, 2004): a 3-item self-report measuring individual's perceived loneliness. Each item is evaluated with scores ranging from 0 (never) to 3 (often), total score is the sum of all items, and higher score indicates higher level of perceived loneliness.

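### No primary efficacy outcome is named for Objective 2, the outcome list is open and every test uses .05, so the chance of a false-positive efficacy result exceeds 5%

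*Combined protocol and SAP*

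**What the plan says.** Objective 2 in the Objectives section is broad: "To evaluate the efficacy of the programme in reducing symptoms/risks and promoting wellbeing in older people at-risk of or with depression". It does not say which measure decides the question.

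The Data Analysis section says that "changes in outcome measures, including PHQ-9 and GAD-7 scores, will be assessed by a three-level linear mixed model". The word *including* leaves the list open. The Measurements section then describes several further scales without sorting them into primary, secondary or descriptive.

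The significance rule is a single sentence: "For all the tests, the statistical significance level was set at .05". No hierarchy, split of alpha or adjustment across outcomes accompanies it.

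One endpoint is called primary. It appears in the paragraph on engagement, as "Cox proportional hazard regression analysis of the time to the primary endpoint of voluntary withdrawal from service", next to a second engagement test, "Chi-square test of initial refusal of service by eligible participants after screening". Both serve Objective 1.

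The Participants section gives group sizes (1,600 + 400 intervention, 400 + 100 control) with no target outcome, effect size or power. The sample size therefore does not reveal an implied primary outcome either.

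**The concern.** A reader of the final report could not tell from the plan which result decides whether the programme works. If PHQ-9 showed nothing and one other scale reached .05, the plan as written would allow that scale to carry the efficacy conclusion.

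The .05 rule is explicit, so this is more than missing detail. Applied as stated to several outcomes that can each satisfy Objective 2, it does not hold the error rate of the efficacy conclusion at .05.

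The plan does care about type I error, since it applies a Satterthwaite correction because there are few clusters. That correction works inside each mixed model and does nothing about the number of models fitted. The project is meant to yield a best-practice model for preventing depression in older people, so the outcome behind the efficacy claim should be fixed in advance.

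**Working it through.** **Inputs from the plan**
- Level per test: .05 (Data Analysis). Sidedness is not stated; two-sided is assumed.
- Outcomes named for the mixed model: PHQ-9 and GAD-7, so the number of tests k is at least 2 (Data Analysis).
- Candidate efficacy measures in Measurements: PHQ-9; self-harm risk, which ends in an "overall evaluation of suicidal risk score ranging from 0-No to 3-High"; GAD-7; HK-MoCA 5-Min; name generator; UCLA-3; EQ-5D-5L; life engagement. That makes k = 8.
- Contrasts per outcome: Assessment Procedures has the control group assessed at T0 and T2 only. One between-group change contrast per outcome is assumed.

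**Left out of the count**
- CSRI, which serves Objective 3.
- The withdrawal and refusal tests, which serve Objective 1.

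**Starting point.** The plan's .05 is a chosen level with nothing to derive. For one test, 1 − 0.95¹ = 0.050, so the rule is sound if a single outcome decides.

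**Independent outcomes, no true effect, significance in either direction:** 1 − 0.95^k
- k = 2: 1 − 0.95² = 0.0975, or 9.8%.
- k = 8: 1 − 0.95⁸ = 0.3366, or 33.7%.

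**Correlated outcomes.** Scales measured on the same people will be correlated, which lowers these figures. Assume jointly normal test statistics with a common correlation ρ and critical value c = 1.96. The chance of at least one significant result is

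1 − ∫ φ(u) · [Φ((c − √ρ·u)/√(1−ρ)) − Φ((−c − √ρ·u)/√(1−ρ))]^k du

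**In the programme's favour only.** Score every outcome so that benefit is positive, and use .025 in that tail. Under independence the formula is 1 − 0.975^k: 1 − 0.975² = 0.0494 and 1 − 0.975⁸ = 0.1833. With correlation, the lower term in the integral is dropped.

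| | ρ = 0 | ρ = 0.3 | ρ = 0.5 | ρ = 0.7 |
|---|---|---|---|---|
| k = 2, either direction | 9.8% | 9.5% | 9.1% | 8.4% |
| k = 8, either direction | 33.7% | 30.0% | 25.0% | 19.1% |
| k = 2, favouring programme | 4.9% | 4.8% | 4.5% | 4.2% |
| k = 8, favouring programme | 18.3% | 15.2% | 12.5% | 9.5% |

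The benchmark for a single test is 5% in either direction and 2.5% in the programme's favour. With two outcomes the either-direction error is 1.7 to 2.0 times nominal (8.4/5 to 9.8/5). With eight it is 3.8 to 6.7 times nominal (19.1/5 to 33.7/5).

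**After the change.** One named primary outcome tested at .05 gives 5.0%. If several outcomes were kept as alternative primaries with Bonferroni, the levels would be .05/2 = .025 each for two and .05/8 = .00625 each for eight. Either choice holds the overall error at about 4.9% under independence.

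**The case against.** **The count of eight is not the plan's.** Only PHQ-9 and GAD-7 are named as modelled outcomes. The Measurements section also lists demographics and a risk screen, so being listed there does not make something an efficacy outcome. Life engagement is described as feeding an exit criterion, and the "Hong Kong Montreal Cognitive Assessment 5-Minute Protocol (HK-MoCA 5-Min") is described as a cognitive screen. This stands: the open wording permits tests of all eight but does not require them. Hence the size is given as a range that starts at two.

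**PHQ-9 is the natural primary in a depression trial and is listed first.** That is reasonable as a guess. But it is listed jointly with GAD-7 in an open list, and the plan attaches "the primary endpoint of voluntary withdrawal from service" to something else.

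**The primary label is already confined to engagement.** The paragraph opens by saying that it concerns engagement, and engagement is Objective 1. This also stands: relabelling withdrawal is a clarification, not the correction of an error.

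**One symptom score does not cover an objective that also includes wellbeing.** True. A hierarchy or adjusted co-primary outcomes would also control the error.

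**Stronger readings that the documents do not support**
- A reader might infer that a false efficacy claim is *likely*. With eight measures the chance stays below 50% even under independence, and it is at most about 18% in the programme's favour. It takes 14 independent tests to pass one half (1 − 0.95¹⁴ = 51.2%).
- A reader might add CSRI (k = 9, 37.0%) or also the two engagement tests (k = 11, 43.1%). A false positive on service use or refusal is not a false claim of efficacy under Objective 2.
- A reader might double the count for the at-risk and symptomatic groups (8 × 2 = 16 gives 56.0%; 9 × 2 = 18 gives 60.3%). Participants sets recruitment numbers for these two groups, but Data Analysis plans no separate tests in them.

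The pages before the Background section were not available, so an outcome ranking there cannot be ruled out. The Objectives, Measurements and Data Analysis sections contain none.

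**Conclusion.** The point holds as a material but bounded inflation of error. For Objective 2 the plan names no primary outcome, leaves the list open and tests everything at .05. The chance of at least one false-positive efficacy result is about 8–10% on the narrowest reading and about 19–34% on the widest. Roughly half of each figure favours the programme (about 4–5% and 10–18%).

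These figures rest on two-sided tests, no true effect on any outcome, one contrast per outcome, and a common correlation between 0.7 and 0. The number of measures tested and the correlations are assumptions. What does not depend on them is that any second efficacy outcome tested at an unadjusted .05 takes the overall error above 5%, unless the tests are perfectly correlated. The change should be made before analysis; it does not call the data collection into question.

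**What to change.** In Data Analysis:

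1. Name the between-group difference in PHQ-9 change from T0 to T2 as the single primary efficacy outcome, tested at two-sided .05. T0 to T2 is the only interval assessed in both groups, so no new data are needed.
2. Replace the open list with a closed one. List the other Objective 2 scales as secondary and report them as estimates with 95% confidence intervals and no stand-alone efficacy claim. Alternatively, test them with a Holm adjustment.
3. Limit the .05 sentence to the primary outcome of each objective, and state that tests are two-sided.
4. In the Cox sentence, label voluntary withdrawal as the primary outcome for Objective 1 only.

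This changes wording in the analysis plan only. The cost is that a secondary scale can no longer support an efficacy claim at an unadjusted .05, and that the wellbeing part of Objective 2 rests on secondary evidence. If the sponsor wants wellbeing to carry equal weight, a prespecified hierarchy or adjusted co-primary outcomes would also control the error, at some loss of power for each outcome.
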